9.6 Data Analyses

We will follow the CONSORT Statement guideline to analyze and report the data from this trial: <http://www.consort-statement.org/consort-statement/>. The primary analyses will be the ITT population, that is, patient intervention status will be analyzed as randomized. As a secondary analytic goal, we will also consider per protocol analysis. Primary hypothesis: *Asthma control as assessed by the Asthma Control Questionnaire will improve more in MBSR than in HLC participants at 18-month follow-up.* We will first analyze the data descriptively by study arm (intervention vs. control) and by time point (e.g., 18 month), report descriptive statistics (mean, SD, lower and upper quartiles, median and range), and test between arm differences using t-test (normally distributed outcomes), Wilcoxon rank sum test (for skewed variables) and Chi2 test statistics (categorical variables, such as occurrence of symptoms). We will carefully examine the distributional characteristics of the outcome variables to identify proper distributional function or statistical transformations for further modeling.

Since the measures are longitudinal, we will also use linear or generalized mixed models to evaluate the intervention effects on ACQ score and presence of symptoms. We will include intervention indicator (MBSR=1 and HLC control=0) in the mixed models to estimate intervention effect. To account for auto-correlations among repeated measures on the same patient, we will include in the mixed models patient level random effects and use either first order autoregressive correlation or unstructured covariance structure for robust estimates. Within physician correlations will be modeled by including physician level random effects. We will also consider inclusion of key physician attributes such as sub-specialty in the models in order to understand how physician factors may influence the intervention effects. Since interventions will be delivered by class, we will model each class as a potential random effect in the model and test if inclusion of the class level random effect improves model estimation. If class level random effect exists, we will fit a two level hierarchical model (repeated measures on patients nested within each class). We will estimate the intervention effects with and without adjusting for patient socio-demographic and clinical co-variables. Covariate adjustments will focus co-variables that are unbalanced between the two arms, or inclusion of them will lead to substantial reduction of

variance in estimates of intervention effects, or those modifying the intervention effects. To test whether intervention effects vary by these factors, we will test the significance of the interactions between intervention indicators and each co-variable. A significant interaction term signals potential variation of intervention effect, which warrants further investigation.

To model presence of any specific component of asthma control at follow-up time points, we will use mixed effects logistic regression models. This analysis is important to understanding whether specific control component worked well or not among patients, and if there is any differential effect between the two arms. To model intervention effects on number of symptoms at each follow-up, we will use mixed effects Poisson regression models. General modeling approaches are similar to those for ACQ scores and thus not repeated, except that the underlying statistical distributions differ.

To assess the heterogeneity of intervention effects, and to identify which patient groups would benefit the most or the least from the interventions, we will conduct subgroup analysis stratified by select patient characteristics (e.g., sex, age group, severity, select symptoms, and ethnicity). We will also consider use of latent group modeling (patient profiling) to identify latent patient response groups (e.g., good responder vs. non-responder). The analysis will be conducted using [name] award-winning approach for profiling patient functional returns after total knee replacement surgeries.¹⁰⁰

Secondary Outcomes: Analytic approaches for asthma-related QoL, respiratory interoceptive accuracy, lung function are generally similar to those for the two primary outcomes. To test the mediation effect of respiratory interoceptive accuracy (RIA) on asthma control, QoL, and medication use, we will first compare the difference in RIA by treatment arm. We will then use difference-to-difference approach to analyze the longitudinal associations of the changes in RIA from baseline to each follow-up time point with changes in ACQ, QoL and medication use from baseline to comparable follow-up time points.¹⁰¹⁻¹⁰³ Since we will have measures on three follow-ups, we will use linear mixed models where ACQ, QoL and medication use are treated as outcomes, RIA as the primary predictor, with and without an interaction term between RIA and MBSR indicator. These analyses will help answer whether MBSR intervention improved RIA, and whether between treatment differences in RIA would explain the observed differences in ACQ, QoL and medication use. We will compute incremental cost-effectiveness of MBSR compared with HLC as the difference in average health care costs per study participant over 18 months between MBSR and HLC, divided by the difference in average ACQ. As planned for another NIH-funded cost-effectiveness study (5R01AA009892-19), we will use the overlap between self-reported and administrative reimbursement data to estimate models of administratively estimated inpatient, outpatient, and medication services data as functions of the self-reported data. We will apply these models to all self-reported data to derive the 18-month health care costs of MBSR and HLC. We will calculate the cost of delivering the MBSR and HLC from the Brief Treatment Cost Analysis Tool (TCAT), a validated costing tool for counseling interventions.⁸⁹ Sensitivity analysis: ICER ratios will be computed between baseline and active comparator, with usual considerations of uncertainty evaluated in a probabilistic sensitivity analysis to determine the level to which our cost-effectiveness conclusions are robust.

To compare the cost-effectiveness in asthma control and management between the comparator arms we will compute per-person incremental total cost per defined measure of additional clinical benefit. More specifically, total costs will include direct and indirect costs of intervention, and per-person overall healthcare/hospital care costs over the entire follow-up period to study completion. Key clinical endpoints will include prevention of exacerbations, unscheduled acute care office visits, and emergency room visits, as well as additional quality of life achieved. We will use general linear models to analyze the associations of the person-level intervention cost with ACQ scores, and use the model to predict per-arm required intervention effects. Secondly, we will use linear models to analyze the associations of person-level intervention cost with total healthcare/hospital care cost, and examine whether increases in intervention cost are correlated with lower average healthcare/hospital care cost. This "return-on-investment" analysis will provide information on monetary savings on care cost per dollar of MBSR intervention. Following these steps, we will apply log-linear models to analyzing the intervention-to-care cost ratios, and examine whether they differ by MBSR/HLC status, and other patient/physician factors.

Missing data: For most longitudinal trial studies, missing data and dropouts are unavoidable. To account for potentially differential/informative dropouts, we will apply inverse probability weighting methods that [name] developed for clinical trial studies with [name] and associates.^{104 #2421, 105} This method first estimates the probability of dropout/lost-to-follow-up of a participant based on his/her sociodemographic and health profiles, and uses the estimated probabilities as weights in the regression analysis. This method effectively removes

potential bias associated with differential lost to follow-up (e.g., unequal rate of lost to follow-up by patient attributes or by intervention conditions) while following the intent-to-treat principle. In addition, this method can be modified to handle potentially non-random missingness, such as dropouts due to poorer outcomes. For example, whether a participant drops out at time point 3 may depend on his/her outcomes at time point 2. The model can be adapted to handle outcome dependent missingness. For missing data on covariates, we propose to use multiple imputation methods that have become the standard approach in clinical trial studies and we routinely apply using Stata MP 13 (Stata Corp., College Station, TX).

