9.2 Sample Size and Randomization

The trial size was determined based on hypothesized intervention effects on ACQ score, the primary outcome. We will recruit 254 individuals, but base power calculations on n=216 (108 per arm) anticipating $\leq 15\%$ loss to follow-up. With one baseline measure and 3 follow-up measures at 6, 12 and 18 months, the trial can detect an intervention effect of 0.25 ACQ score improvement using ANCOVA (or linear mixed models) method at 5% significance level and at least 80% power. This treatment effect is consistent with recent reported drug-trials for asthma control. Based on literature, for sample size estimation we assumed the mean (SD) of ACQ scores for the MBSR and HLC groups are 1.24 (0.66) and 1.49 (0.66) averaged over the three follow-up time points, respectively, and a serial correlation of 0.45 within patients. We expect to recruit patients from 12 physicians at each site, with on average each physician contributing 9 patients. Because within physician correlation has not been reported in literature and our small-sized pilot study does not allow an accurate estimation, we conservatively assumed a modest within physician correlation of 0.05. The sample size was estimated using Stata MP 12.

Our sample size estimation and power analysis are conservative and the treatment effect is chosen for other important reasons: a) to preserve the possibility of addressing treatment heterogeneity by select patient and physician characteristics (e.g. differential effects between male and female participants, ethnicity); we plan to conduct subgroup analysis and examine how treatment effects may differ. Such analysis will be very important when refining the treatment protocols and for dissemination if proved effective; b) other than the primary outcome, we are also interested in other primary/secondary outcomes described below and powered the trial to detect meaningful changes in these outcomes as well. The sample size is determined to allow us to achieve all these analytic goals, not just for the primary outcome.

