9.5 Outcomes

9.5.1 Primary Outcome: The primary objective is to evaluate the effect of MBSR in improving asthma control as assessed by the Asthma Control Questionnaire. *Hypothesis: Asthma control as assessed by the Asthma Control Questionnaire³ will improve significantly more in MBSR than in HLC participants at 18 month follow-up.*

9.5.2 Secondary Outcomes:

1) Asthma-related QoL. *Hypothesis: Asthma-related QoL (AQoL)⁴ will improve more in MBSR than HLC participants from baseline to 18-month follow-up.*

2) Respiratory interoceptive accuracy and its mediating effect on asthma control, QoL, and medication use. *Hypotheses: MBSR will result in improved accuracy (Breath Perception Discrimination Test) at 6-, 12- and 18-months compared with HLC, and will be correlated with improved asthma control, QoL, and medication use.*

3) Lung function (change from baseline in 2-week average morning peak expiratory flow (PEF) and spirometry (Forced Expiratory Volume in 1 second (FEV₁)) at 6-, 12- and 18-months compared with HLC. *Hypotheses: There will be no deterioration, and possibly improvement, in lung function in MBSR participants from baseline to 6-, 12- and 18-months as measured by PEF and FEV₁ as compared with HLC.*

4) Cost-effectiveness in asthma control and management. *Hypothesis: MBSR will be associated with improved cost-effectiveness and improved cost-utility by 18 months as compared with HLC. This will be based on clinical outcomes (e.g., asthma control, QoL, medication use) as well as quality-adjusted life years.*

To conduct cost analysis, we will collect data on number of moderate and severe exacerbations, asthma-related regularly scheduled office visits, acute care visits, hospitalizations, emergency room visits, need for intubation or mechanical ventilation, and other costs during the prior 6 months at baseline, 6-, 12- and 18-month follow-up and associated clinic and hospital costs. The cost data will be determined by two methods: Self-report and actual hospital and health system costs (direct and indirect) obtained from administrative reimbursement data (see Letters of Support from fiscal offices). Brief Treatment Cost Analysis Tool (TCAT), a validated costing tool for counseling interventions,⁸⁹ will be used to calculate cost of delivering MBSR and HLC.

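### The primary ACQ hypothesis is set at 18 months, but section 9.6 names no primary test and section 9.2 states power only for the average of three visits

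*Combined protocol and SAP*

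**What the plan says.** The précis and sections 1.1, 9.1, 9.5.1 and 9.6 all put the primary comparison at 18 months. In 9.5.1 the claim is that ACQ-assessed control "will improve significantly more in MBSR than in HLC participants at 18 month follow-up".

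Section 9.6 then describes more than one analysis of ACQ:

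- A first step, "We will first analyze the data descriptively by study arm (intervention vs. control) and by time point (e.g., 18 month"), which includes a t-test or a Wilcoxon test, depending on the distribution.
- A model step: "Since the measures are longitudinal, we will also use linear or generalized mixed models to evaluate the intervention effects on ACQ score". The treatment term is given as: "We will include intervention indicator (MBSR=1 and HLC control=0) in the mixed models to estimate intervention effect". For the correlation between visits the plan will "use either first order autoregressive correlation or unstructured covariance structure for robust estimates". A class random effect is kept if it improves the model, and effects are estimated with and without covariates.

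Neither step is called primary. No visit term, arm-by-visit term or baseline ACQ term is written.

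Section 9.2 sizes the trial "using ANCOVA (or linear mixed models) method at 5% significance level and at least 80% power"; ANCOVA does not reappear in 9.6. The assumed ACQ means and SDs "are 1.24 (0.66) and 1.49 (0.66) averaged over the three follow-up time points", with a serial correlation of 0.45. No power is given for 18 months alone.

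**The concern.** A mixed model whose only treatment term is the arm indicator assumes that the arm difference is the same at 6, 12 and 18 months. The programme lasts 8 weeks and starts within 8 weeks of randomisation, so the 18-month visit falls about a year or more after the last class. Whether any benefit persists that long is what the primary hypothesis asks, and a common-effect model takes persistence for granted. As an illustration with an assumed profile, differences of 0.30, 0.20 and 0.10 at the three visits average (0.30 + 0.20 + 0.10)/3 = 0.20, twice the 18-month difference.

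If the pooled effect and the 18-month contrast disagreed, the plan would not say which decides the trial, and the choice could be made after results are seen. The power statement does not help, because it describes the average and not the 18-month contrast.

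**Working it through.** **Inputs, all from 9.2:** difference 1.49 − 1.24 = 0.25; SD 0.66; serial correlation r = 0.45; one baseline and three follow-ups; 108 per arm; 5% level.

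**Assumptions:** the test is two-sided (9.2 does not say), and the same difference, SD and correlation hold at 18 months (the documents give none specific to that visit). No inflation for physician is applied, because patients are randomised individually.

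**Formulas.** SE = SD × √(f × 2/108), where SD is the single-visit SD and f is the variance factor after baseline adjustment. Power = Φ(0.25/SE − 1.96). Detectable difference at 80% power = (1.96 + 0.842) × SE.

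**Variance factors, equal correlation**
- Mean of three visits, unadjusted: (1 + 2 × 0.45)/3 = 0.6333
- Mean of three visits, baseline-adjusted: 0.6333 − 0.45² = 0.4308
- 18 months, baseline-adjusted: 1 − 0.45² = 0.7975

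**Variance factors, first-order autoregressive, 0.45 per 6-month step**
- Mean of three visits, unadjusted: (3 + 4 × 0.45 + 2 × 0.45²)/9 = 0.5783
- Correlation term of baseline with the mean: (0.45 + 0.45² + 0.45³)/3 = 0.2479; adjusted factor 0.5783 − 0.2479² = 0.5169
- 18 months: baseline correlation 0.45³ = 0.0911; factor 1 − 0.0911² = 0.9917

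**What 0.66 refers to.** If it is a single-visit SD, it is used directly. If it is the SD of the three-visit mean, the single-visit SD is 0.66/√0.6333 = 0.829 (equal) or 0.66/√0.5783 = 0.868 (autoregressive).

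**The plan's own figure first.** A simple two-mean comparison with SD 0.66 gives SE = 0.66 × √(2/108) = 0.0898 and power 79.5% (110 per arm for 80%). The visit-averaged, baseline-adjusted analysis gives 84% to 99% (last column below). The claim of at least 80% is therefore reproduced for the average. The dropout allowance also agrees: 216/0.85 = 254.1.

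**18-month contrast**

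| Reading of 9.2 | SE | 0.25/SE | Power at 18 months | Detectable difference | Power, visit average |
|---|---|---|---|---|---|
| Equal, single-visit SD | 0.0802 | 3.117 | 88% | 0.22 | 99% |
| Autoregressive, single-visit SD | 0.0894 | 2.795 | 80% (79.8%) | 0.25 | 97% |
| Equal, SD of three-visit mean | 0.1008 | 2.481 | 70% | 0.28 | 92% |
| Autoregressive, SD of three-visit mean | 0.1176 | 2.126 | 57% | 0.33 | 84% |

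First row in full: SE = 0.66 × √(0.7975 × 2/108) = 0.0802; 0.25/0.0802 = 3.117; Φ(3.117 − 1.96) = 0.876.

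**Check on leaving out physician inflation.** With 24 physicians of 9 patients each, within-physician correlation 0.05 and 1:1 randomisation within site, 10,000 simulated trials per reading gave 18-month power of 0.870, 0.791, 0.695 and 0.555, in the order of the table. These are close to the uninflated values.

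**The case against.** **Visit-specific effects may be intended.** Section 9.6 says of symptom counts: "To model intervention effects on number of symptoms at each follow-up, we will use mixed effects Poisson regression models", and describes the approach as similar to that for ACQ. The by-time-point t-test would also give an 18-month comparison. Both are fair points about intent. But no visit-specific term is written for ACQ, and the t-test sits in a step introduced as descriptive.

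**The sizing may be adequate.** Section 9.2 calls it conservative, and giving a serial correlation alongside the number of follow-ups fits a single-visit SD better. On that reading 18-month power is 80% to 88%. This may well be right, but the text attaches the SD to the three-visit average and does not settle it.

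**Blinding gives some protection.** Section 6.2.3 keeps the arms coded A and B, and the statistician blinded, until the main outcomes analysis is complete. That limits choosing a result by its direction. It does not fix which contrast decides the trial.

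**Stronger readings a reader might infer, which the documents do not support:**
- *The trial is underpowered at 18 months.* The 9.2 inputs allow readings on both sides of 80%.
- *Power should be cut further by a full physician design effect from the 0.05 correlation.* That inflation suits allocation by physician. Here patients are randomised individually, and the simulation shows almost no loss.
- *Section 1.1 adds symptoms as a further primary outcome.* The table in 6.2 lists the ACQ as the only primary outcome, and its score already contains five symptom items.

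**Conclusion.** The point holds and should be settled before ACQ results by arm are examined. The primary hypothesis concerns 18 months; the ACQ model as written estimates an effect pooled over visits; no analysis is designated primary.

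The power claim in 9.2 is sound for the visit average but is not shown to apply to the primary hypothesis. Under the assumptions listed above, 18-month power lies between 57% and 88%, and the spread comes entirely from two things that 9.2 leaves open: what the SD of 0.66 describes and which correlation pattern is meant. The conclusion about the missing primary test rests on the text alone and does not depend on these figures.

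**What to change.** **Section 9.6.** Name one primary analysis: a repeated-measures model of ACQ at 6, 12 and 18 months with arm, visit, arm-by-visit and baseline ACQ, unstructured within-patient covariance (one of the two options already offered) and the planned physician random effect. Say in advance whether the class effect is included. The primary test is the arm contrast at 18 months, two-sided 5%. Label the t-test or Wilcoxon test, the visit-averaged effect and models with further covariates as supportive.

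**Section 9.2.** State whether 0.66 is a single-visit SD or the SD of the three-visit mean, and which correlation pattern applies. Then give power for the 18-month contrast as the one figure that matches.

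**Outcome count.** The secondary-outcomes paragraph of 9.6 counts two primary outcomes, and 9.2 mentions further primary or secondary outcomes. Bring both into line with the single primary outcome in 9.5.1 and the table in 6.2.

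**Cost.** The changes are wording plus one recalculation; no new data, visits or patients are needed to make them. The downside is that the stated power for the primary hypothesis may fall below 80%. If 0.66 is the SD of the three-visit mean, 80% power at 18 months would need 138 (equal correlation) or 188 (autoregressive) completers per arm against the 108 planned, or acceptance of a detectable difference of 0.28 or 0.33. The alternative is to make the visit average the primary target, which 9.2 already powers; that would mean rewriting the 18-month hypothesis in the précis, 1.1, 9.1, 9.5.1 and 9.6.

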Design and Outcomes: This is a 5-year randomized controlled trial to evaluate the effect of MBSR on asthma symptom management as reflected in level of asthma control at 18-month follow-up. Two hundred and fifty four patients 18 years and older with documented mild, moderate or severe asthma^{1,2} will be recruited from the patient population of UMass Memorial Health Care (UMMHC) and the Miriam Hospital. Respiratory and psychosocial assessments will be at baseline, and 6- 12-, and 18-months post-baseline.

Interventions and Duration: MBSR will be compared to the Healthy Living program that controls for time, attention and participant demands. Each participant will be on-study for a period of 18 months.

Sample Size and Population: The study sample of two hundred and fifty-four patients will be drawn from a population of individuals eighteen years and older with a documented diagnosis of mild, moderate or severe asthma from a physician. Participants will be randomized to either MBSR or the HLC control. Randomization will be stratified by site and asthma severity with each stratum in randomly allocated block sizes of two using the ralloc program in Stata. The randomization will be carried out within each cohort to ensure the effects of seasonality and temporal trends be adequately controlled by design.

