4.3 Study Enrollment Procedures

Study population: We will recruit 254 participants from the pool of patients at the UMass Memorial Health Care (UMMHC) and Miriam Hospital to provide a total of 216 patients at 18-month follow-up. UMMHC is the clinical partner of UMMS and the largest health care system in Central and Western Massachusetts. There are 17 pulmonologists in the Lung and Allergy Center, and approximately 3,510 patients (Caucasian 78%, non-Caucasian 22%) with a diagnosis of asthma and prescribed an inhaled steroid. UMMS has experience through the NIH-funded pilot study in successfully recruiting patients with asthma into a randomized controlled trial. Miriam Hospital is part of the Lifespan Corporation and is the largest healthcare provider in the state of Rhode Island; their asthma clinic is a critical tertiary asthma clinic that serves the entire state. The network has 37 pulmonologists on staff and 2,778 outpatients with a clinical diagnosis of asthma (Caucasian 68%, non-Caucasian 32%). The respiratory therapist on this team has been involved with recruitment and education in asthma research, and is currently involved with other research projects.

Recruitment procedures: Participants will be recruited to 13 cohorts over 13 quarter periods, with roughly 10-11 participants per cohort. While minor adaptations to the recruitment protocol will be made to cater to institutional arrangements at each site, recruitment procedures will be similar to the successful procedures used in the pilot. The Project Director, [name], will oversee recruitment at both sites.

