Participants will be given ample opportunity to ask questions before giving their consent and all of the potential subject's questions will be answered. While the consent process is expected to take 20-30 minutes, we will minimize the possibility of coercion or influence by providing subjects up to one hour to decide about participation and ample opportunity to reconsider their decision. They will have the opportunity to opt out at the interview or at any point on the study day, including while the study is underway.

The RA conducting the process will determine that the subject understands the information provided and is capable of making and communicating an informed consent. If they still wish to enroll they will complete the written informed consent document (contained in a separate document from this protocol).

Copies of the signed consent form and HIPAA document are retained by the participant and the Project Director. The date of signing will be considered their study enrollment date. This date will be recorded on the study participant's case report form. Forms will be kept in locked filing cabinets separate from all data. All individuals responsible for obtaining consent will have up to date CITI training.

After providing written consent participants will complete the baseline assessments described in Table 6.2.

After all baseline assessments are completed, participants will be randomly assigned to one of the two study arms. Randomization will be stratified by site and asthma severity (see table below) with each stratum in randomly allocated blocks of two using the ralloc program in Stata.^{82, 83} The RA will generate the random allocation sequence, will communicate randomization status to each participant at time of randomization and the allocation table will be uploaded to the RedCap database. Participants in each cohort will be randomized altogether and sent to the same MBSR and HLC classes. This approach is necessary to ensure that the seasonality and temporal differences be balanced between the two arms. We anticipate participants will begin their treatment program (MBSR or HLC) within 8 weeks of randomization.

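### Section 9.6 leaves out the cohort within which patients are randomised, so if class effects are retained, variation shared by both arms is charged to the treatment contrast and power is lost

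*Combined protocol and SAP*

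**What the plan says.** **Design.** The Précis gives the purpose of the blocking: "The randomization will be carried out within each cohort to ensure the effects of seasonality and temporal trends be adequately controlled by design". Section 6.2.2 describes the mechanics, "Participants in each cohort will be randomized altogether and sent to the same MBSR and HLC classes", and adds: "This approach is necessary to ensure that the seasonality and temporal differences be balanced between the two arms". Sections 4.3 and 11.2 repeat the point. Section 4.3 sets the scale: "Participants will be recruited to 13 cohorts over 13 quarter periods, with roughly 10-11 participants per cohort".

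**Analysis.** Section 9.6 lists the following for the longitudinal ACQ models:
- Patient random effects with a serial correlation structure.
- Physician effects: "Within physician correlations will be modeled by including physician level random effects".
- A conditional class effect: "we will model each class as a potential random effect in the model and test if inclusion of the class level random effect" improves the model. If it does: "If class level random effect exists, we will fit a two level hierarchical model (repeated measures on patients nested within each class").
- Covariates: "We will estimate the intervention effects with and without adjusting for patient socio-demographic and clinical co-variables". These are chosen by imbalance, variance reduction or effect modification.

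Section 9.6 names no cohort, quarter, calendar-time or season term. Nothing links the MBSR and HLC classes of the same cohort. The simple between-arm tests at the start of 9.6 do not use cohort either. Section 6.2 collects self-reported months of worse asthma, but no model is said to use them.

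**The concern.** The MBSR and HLC classes of one cohort run in the same quarter and are assessed at about the same calendar times. Anything that shifts the whole cohort (season, a pollen year, a change in practice) affects both arms and cancels in the difference between them. A model with independent class effects and no cohort term cannot see this pairing. It reads the shared shift as variation between classes, unrelated across arms, and adds it to the error of the treatment contrast.

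Two things are at stake. Power for the 18-month ACQ comparison falls in the situation that justified randomising by cohort, namely when season or time trend matters. In addition, a calendar effect may be reported as a class (instructor or group) effect.

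**Working it through.** **1. The plan's own figure (section 9.2).** Inputs: difference 0.25, SD 0.66, 5% level (taken as two-sided), 108 per arm, serial correlation 0.45, physician correlation 0.05 with 9 patients each.
- Plain two-sample comparison: 2 × (1.96 + 0.8416)² × 0.66² / 0.25² = 109.4, so 110 per arm. Power at 108 per arm is 79.5%.
- ANCOVA with three follow-ups: variance factor (1 + 2 × 0.45)/3 − 0.45² = 0.431. Design effect 1 + 8 × 0.05 = 1.40. Power is 94.8%.
- Retention: 254 × 0.85 = 215.9.

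The stated 80% or more is reproduced. Neither cohort nor class variance enters it.

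**2. Layout assumed.** Thirteen cohorts of 10–11 give about 137, not 254, so the cohort size in 4.3 reads as a per-site count (127/13 = 9.8). With one class per arm, that is 13 × 2 sites × 2 arms = 52 classes. Four analysed per class gives 208 patients, 104 per arm.

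**3. Standard errors in closed form.** Let s be the cohort SD, shared by both arms and both sites. It is not in the documents. Total variance is 0.66² = 0.4356, with no true class effect and no baseline adjustment.
- True SE, where cohort cancels: √[2(0.4356 − s²)/104].
- Independent class effects always kept: √[2(s²/26 + (0.4356 − s²)/104)].
- Class dropped: √[2 × 0.4356/104] = 0.0915, whatever s is.

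| s | Share of variance | True SE | Class always kept | Class dropped ÷ true |
|---|---|---|---|---|
| 0.10 | 2.3% | 0.0905 | 0.0946 | 1.01 |
| 0.15 | 5.2% | 0.0891 | 0.0984 | 1.03 |
| 0.20 | 9.2% | 0.0872 | 0.1034 | 1.05 |
| 0.30 | 20.7% | 0.0815 | 0.1165 | 1.12 |

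**4. The planned procedure.** Section 9.6 tests class first, so step 3 alone does not describe it. Each setting was simulated 20,000 times: F-test of class at 5% (an assumed level), keep or drop, then test the arm.

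| s | Class retained | SE too wide by | Power, planned | Power, cohort term |
|---|---|---|---|---|
| 0.10 | 11% | 3% | 76% | 78% |
| 0.15 | 22% | 7% | 75% | 79% |
| 0.20 | 43% | 14% | 72% | 81% |
| 0.30 | 85% | 39% | 60% | 86% |

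Type I error of the planned procedure is about 3% at s = 0.2 and 1% at s = 0.3, below the nominal 5%.

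**5. With baseline adjustment at 18 months.** SD becomes 0.66 × √(1 − 0.45²) = 0.589. With 108 per arm, 26 class pairs, a 5% cohort share and class kept, the SE is 0.086 instead of 0.078, and power is 83% instead of 89%.

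**6. With a real class effect.** With class SD 0.1 and s = 0.2, planned power is 69%. Cohort plus nested class gives 77% with type I error 5.1%. Cohort without class gives 6.1%, so the cohort term should not replace the class effect.

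**The case against.** **Class is not fixed in the model.** A reader might infer that the standard errors will be too wide in any case. The documents do not support that, because class is only a candidate and depends on a test. In the simulation it is dropped in most trials at s = 0.1 to 0.2. Once it is dropped, cohort variation adds little, and if a real class effect is missed the SE can be too narrow: 0.86 to 1.02 times the true value for a class share of 2–5%. This stands, and it is why the sizes above come from the tested procedure.

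**The design still does its work.** A reader might also infer that the analysis throws away the control of season, or that the result is biased. It does not. Randomising within cohort balances season whatever model is fitted, and the error is conservative. This stands in full.

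**The size rests on an unknown.** No cohort variance is given, and s = 0.3 would be a fifth of all ACQ variance. At about 2% there is practically nothing to gain. This stands.

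**Annual season partly cancels.** The 6- and 18-month visits fall in one season and the 12-month visit in the opposite one. A purely annual effect x therefore averages to (x − x + x)/3 = x/3, or 1/9 of the variance. For a seasonal share of 5–10% per visit, inflation is then about 2–4% with 26 class pairs and 4–7% with 13. This stands for a three-visit average. It does not help the 18-month contrast that the primary hypothesis names, or trends across the 13 quarters.

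**The covariate clause might admit cohort.** It concerns patient characteristics. A balanced blocking factor would not enter through imbalance, and adding it later because it reduces variance would be a data-driven choice. This does not close the gap.

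**Conclusion.** The concern holds as a matter of efficiency. Cohort is a randomisation block shared by both arms and is missing from the section 9.6 models. When independent class effects are retained, cohort variation is counted as error in the arm contrast, so the SE is too wide and power is lost. Validity is not at issue.

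Under the stated assumptions the loss is about 2 percentage points of power at a cohort SD of 0.1 (78 − 76), 4 at 0.15, 9 at 0.2 and 26 at 0.3. It rests on the assumed cohort SD, a 5% test for class, one class per arm per site and cohort, no true class effect and no baseline adjustment. Section 5.1 offers two class schedules, so the class count may differ. With baseline adjustment, power can stay above the planned 80%, as in step 5.

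**What to change.** In section 9.6:
- Prespecify a cohort term in the ACQ and secondary-outcome models: quarter, or site-by-quarter if cohorts are site-specific. State which definition applies.
- For the 18-month contrast, let the cohort term vary by visit, or replace it with calendar quarter of visit.
- Nest the class random effect within cohort, site and arm, and assess or retain it only after cohort is in the model.

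**Cost.** Analysis wording only, with no new data. As fixed effects the term uses 13 − 1 = 12 degrees of freedom, 26 − 1 = 25 if cohorts are site-specific, or about 12 × 3 = 36 with cohort-by-visit terms over three follow-ups. About 216 patients are expected to be analysed. A random cohort effect avoids most of this cost.
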